8.3.2 Telephone Contact After Experimental Sessions

The goal of the telephone contact is to assess health changes, ensure participant safety, and offer support. The therapy team will follow-up with the participant by telephone on Days 2, 4, 6, 7, 8, 10, 12, and 14 after each Experimental Session. Each call will last on average 5 to 20 minutes but could be longer to address participant concerns and to adequately assess wellbeing. Additional telephone contact can be initiated at the request of the therapy team or participant. If any planned phone contact would occur on the date of an Integrative Session, the phone contact does not need to be completed.

At each telephone contact, the therapy team will:

- Inquire about any possible changes in health, assess the participant's mental health and the status of any previously recorded AEs, and record AEs as described in [Section 11.0 Safety](#).
- Inquire about concomitant medication use and adherence.
- Offer support in accordance with the Treatment Manual.
- Administer the Since Last Visit C-SSRS.

8.3.3 Integrative Sessions

After each Experimental Session, three Integrative Sessions will take place. Each session will consist of 90 minutes of psychotherapy. Integrative Sessions should not be less than 48 hours apart.

Treatment 1

- Integrative Session 1.1 (Visit 6): morning after Experimental Session 1 (Visit 5)
- Integrative Session 1.2 (Visit 7): 3 to 14 days after Experimental Session 1 (Visit 5)
- Integrative Session 1.3 (Visit 9): 20 to 34 days after Experimental Session 1 (Visit 5) and 1 to 7 days in advance of Experimental Session 2 (Visit 10). This visit serves two purposes: to continue integration and to prepare for the next Experimental Session. The participant will complete the LEC-5 self-report measure.

Treatment 2

- Integrative Session 2.1 (Visit 11): morning after Experimental Session 2 (Visit 10)
- Integrative Session 2.2 (Visit 12): 3 to 14 days after Experimental Session 2 (Visit 10)
- Integrative Session 2.3 (Visit 14): 20 to 35 days after Experimental Session 2 (Visit 10) and 1 to 7 days in advance of Experimental Session 3 (Visit 15). This visit serves two purposes: to continue integration and to prepare for the next Experimental Session. The participant will complete the LEC-5 self-report measure.

Treatment 3

- Integrative Session 3.1 (Visit 16): morning after Experimental Session 3 (Visit 15)
- Integrative Session 3.2 (Visit 17): 3 to 14 days after Experimental Session 3 (Visit 15)
- Integrative Session 3.3 (Visit 18): 21 to 35 days after Experimental Session 3 (Visit 15). This visit will be the final Integrative Session prior to entering the follow-up period. The participant will complete the LEC-5 self-report measure.

During Integrative Sessions, the therapy team will:

- Record the session.
- Inquire about any possible changes in health. Assess the participant's mental health and the status of any previously recorded AEs. Record AEs as described in [Section 11.0 Safety](#).
- Inquire about concomitant medication use and adherence.
- Administer Since Last Visit C-SSRS to determine suicidal risk.
- Discuss and review events that occurred with the participant during the Experimental Session, including thoughts, feelings, and memories. If necessary, the therapy team will help the participant to reduce any residual psychological distress they are experiencing. The therapy teams will also encourage the transfer of states of acceptance, feelings of intimacy, closeness, and reduced fear experienced in Experimental Sessions to emotionally threatening everyday situations. The therapy teams will be supportive, validate the experience, and facilitate understanding and emotional clearing.
- Be accessible for additional support via phone or telemedicine if needed.
- At each third Integrative Session, direct the participants to complete the LEC-5.

8.3.4 Independent Rater Assessments

Participants will have two CAPS-5 assessments during the treatment period of the study (Visits 8 and 13). A blinded IR from the IR Pool will conduct the assessments via telemedicine. These assessments may be recorded to establish inter-rater reliability. The results will not be sent to site staff but instead will be sent to a blinded IR Coordinator to enter the data which will be blinded to sponsor and site personnel. Participants will be instructed to withhold their opinion on treatment group assignment or the number of study visits they have completed from IRs. The IR will also administer the DSP-I and SDS at these time points.

An Integrative Session and CAPS-5 assessment may take place on the same day (in the appropriate order, per protocol). The assessments will be scheduled as follows:

- CAPS-5 T2 (Visit 8): 18 to 30 days after Experimental Session 1 (Visit 5), between Integrative Session 1.2 (Visit 7) and Integrative Session 1.3 (Visit 9)
- CAPS-5 T3 (Visit 13): 18 to 30 days after Experimental Session 2 (Visit 10), between Integrative Session 2.2 (Visit 12) and Integrative Session 2.3 (Visit 14).

8.4 Follow-up Period and Study Termination

8.4.1 Follow-up Period

After the last Integrative Session 3.3 (Visit 18), participants will enter follow-up for approximately 4 weeks (± 2 weeks) with no protocol required visits until the final CAPS-5 assessment (Visit 19) followed by Study Termination (Visit 20). Participants will have access to therapy teams for support if needed, and additional visits via phone, telemedicine, or in person can be scheduled if requested. Participants will continue to comply with protocol requirements for concomitant medications until after Study Termination.

8.4.2 Final Independent Rater Assessment

Participants will have a final CAPS-5 assessment at the completion of the follow-up period (Visit 19). A blinded IR from the IR Pool will conduct the assessments via telemedicine. These assessments may be recorded to establish inter-rater reliability. The results will not be sent to or seen by site staff but instead will be sent to a blinded IR Coordinator to enter the data which will also be blinded to the sponsor. Participants will be instructed to withhold their opinion on treatment group assignment from IRs. Although there are allowable windows for all visits throughout the protocol, the Primary Outcome CAPS-5 T4 assessment is targeted to be completed 18 weeks (± 3 weeks) (105 to 147 days) after the Baseline CAPS-5 assessment (Visit 3) and 8 weeks (± 2 weeks) (42 to 70 days) after Experimental Session 3 (Visit 15). If there are significant delays in the timing of Experimental Session 2 (Visit 10) and/or Experimental Session 3 (Visit 15), the visit should be scheduled 8 weeks (± 2 weeks) (42 to 70 days) after Experimental Session 3 (Visit 15). Participants who have withdrawn from treatment will also complete a final CAPS-5 assessment immediately upon withdrawal. The IR will also administer the DSP-I and SDS.

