This blinded study will compare the effects of a flexible dose of MDMA or placebo administered in three Experimental Sessions. Initial doses per Experimental Session range from 80 mg to 120 mg of MDMA compounded with inactive excipients or indistinguishable weight placebos comprised entirely of inactive excipients, followed 1.5 to 2 hours later by a supplemental half-dose (40 mg or 60 mg, or placebo). A flexible dosing regimen was chosen to mimic proposed clinical practice and better adapt to risk-benefit considerations. The initial active doses of 80 mg and 120 mg are expected to produce all commonly reported effects of MDMA. The supplemental half-dose will prolong subjective effects of MDMA without producing physiological effects much greater than peak effects occurring after the initial dose, and will be administered unless contraindicated. Total amounts of MDMA to be administered per Experimental Session range from 80 mg to 180 mg.

An inactive placebo has been selected as the control to allow differentiation of any additional MDMA effect from psychotherapy alone. This pivotal study will generate unequivocal assessment of safety data and demonstration of efficacy of MDMA-assisted psychotherapy compared to psychotherapy plus placebo.

Table 3: Dose Regimen of MDMA or Placebo

Experimental Session	Initial Dose	Supplemental Dose*	Min-Max Cumulative Dose
1	80 mg	40 mg	80 mg to 120 mg
2	80 or 120* mg	40 or 60 mg	80 mg to 180 mg
3	80 or 120* mg	40 or 60 mg	80 mg to 180 mg
Total Cumulative Dose			240 mg to 480 mg

* Unless contraindicated

In the first Experimental Session, the initial dose will be 80 mg MDMA or placebo. In the second and third Experimental Sessions, the initial dose may be increased to 120 mg MDMA or placebo unless contraindicated in the opinion of the site team. The choice of whether to keep the dose the

same or change it from the first Experimental Session will be made by the site team based on observed response, tolerability to the previously administered dose, and discussion with the participant. In each Experimental Session, 1.5 to 2 hours after the initial dose is given, the participant will be administered a supplemental half-dose unless contraindicated. Participants will not know if they have been assigned MDMA or placebo but can indicate if they want the dose to change or remain the same.

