each symptom according to standard CAPS-5 procedures. Doing so ensures that all symptoms contributing to the CAPS-5 PTSD diagnostic status and total severity score are either temporally or functionally related to the index trauma rather than attributable to non-trauma current life stressors or current world events such as the COVID-19 pandemic. Avoiding a biased administration can be achieved by adhering to administration guidelines verbatim and only deviating from the script to clarify, re-direct, or query further if behavioral examples are needed to determine the appropriate symptom intensity rating. Avoiding building therapeutic/clinical rapport beyond the basic level of rapport needed to conduct the interview in the research setting also minimizes the chance for bias. Remote assessment assures that the rater who is collecting the Primary Outcome will not witness Experimental Sessions and the acute effects of IMP, which strengthens the study blind. Interviews may be recorded in as many instances as necessary to establish reliability of a random selection of interviews for accuracy. After the initial screening visit, the IRs will be blinded to visit number, number of treatments received, treatment assignment, and any study data for the participant. IR visits will be assigned based on availability.

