9.4 Blinding and Bias Minimization

Eligibility will be determined by review of screening by the PI, site team and as needed the sponsor Medical Monitor prior to randomization. Participants, site staff, and the sponsor will remain blinded to subject group assignment until after the database is locked.

To further minimize bias in measuring efficacy, the sponsor will use an observer-blind, centralized, reliable IR pool to administer the Primary Outcome measure via live video interviews. The IR Pool will have no knowledge of AEs and will only evaluate participants at Baseline and at the assessments scheduled after each Experimental Session. The IR Pool is blinded to full study design, visit number, treatment assignment, number of treatments, and any data from the treating therapy team after Baseline. IRs will be assigned to participants based on availability. Participants will be instructed to withhold their opinion on treatment group assignment from IRs. The participants, sponsor, and site staff will not see the CAPS-5 results until the end of the study. Timing of CAPS-5 assessments are pre-specified in the study protocol within visit windows. Changes in study management and analysis, if any, will be made by sponsor personnel who are blinded to group assignment and CAPS-5 data.

As a site-independent review method that evaluates and confirms diagnoses, symptom severity, and subject validity prior to randomization, the Senior IR will review video recordings of actual clinical interviews conducted by the IR Pool. The recordings of these interviews accompanied by digital notes will be electronically submitted for independent review and 'dual' scoring of key rating instruments. This site-independent Senior IR reviewer either affirms subject eligibility or identifies administrative and/or clinical issues that may preclude study eligibility (screen failure). The Senior IR reviewer will invite the study team (including therapists, site physician, and Clinical Investigator) to provide any additional information that may inform the Senior IR reviewer's opinion. The Senior IR reviewer will make the final judgment on whether or not the participant has an exclusionary diagnosis.

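### The instruction to participants at the rating visits is narrower than the rater blind the protocol promises, narrowest at the primary endpoint visit, and no check of that blind is planned

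*Protocol*

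**What the plan says.** **Instruction to participants.** Protocol Section 8.4.2, on the Visit 19 rating: "Participants will be instructed to withhold their opinion on treatment group assignment from IRs". Section 9.4 carries the same sentence. Section 8.3.4, on Visits 8 and 13, goes further: participants are to "withhold their opinion on treatment group assignment or the number of study visits they have completed from IRs". No section asks them to keep back what happened in Experimental Sessions, or effects or side effects of the study drug.

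**Promised blind.** Section 7.1.1 says that, after initial screening, raters are "blinded to visit number, number of treatments received, treatment assignment, and any study data for the participant". Section 9.4 describes the pool as "blinded to full study design, visit number, treatment assignment, number of treatments" and adds: "The IR Pool will have no knowledge of AEs".

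**Contrast between arms.** Under Section 5.5 the control is an inactive placebo, while the initial active doses of 80 and 120 mg "are expected to produce all commonly reported effects of MDMA".

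**Other safeguards.** Sections 5.1, 7.1.1 and 9.4 provide for remote video rating, a neutral scripted interview with little rapport, allocation of raters by availability, no rater access to site data, and a separate database for rater scores.

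**Checks.** Neither document plans a treatment guess, a log of disclosures or an analysis of the rater blind. Section 8.4.2 makes recording optional and gives inter-rater reliability as its purpose. Senior-rater monitoring (Protocol 9.4, SAP 6.0) covers logic and reliability, transcription errors and data trends.

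**The concern.** Blinded central rating is the plan's main protection for the CAPS-5 primary endpoint and the SDS key secondary endpoint, because acute effects are likely to tell many participants and therapists the arm. The remaining route to the rater is the participant, who talks with the rater live for about an hour.

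On that route the wording is weakest at the visit that decides the trial. It omits an element that the earlier visits include, and at every visit it omits what most plainly distinguishes the arms. A description of what a capsule did is not an opinion on assignment, so it falls outside the instruction. If raters learned the arm this way, scores could drift toward expectation, and no planned data would show whether that had happened.

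**Working it through.** **1. Instruction against promise.**

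| What could be disclosed | 8.3.4 (Visits 8, 13) | 8.4.2 (Visit 19) and 9.4 | Promise in 7.1.1 and 9.4 |
|---|---|---|---|
| Opinion on assignment | covered | covered | blind to assignment |
| Visit count | covered | not covered | blind to visit number and number of treatments |
| Session experiences, drug effects | not covered | not covered | blind to assignment and study data |
| Side effects | not covered | not covered | no knowledge of adverse events |

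The last two rows matter most. Both arms are scheduled for three Experimental Sessions, so a count says little about the arm. A described drug effect can say a great deal when the comparator is inactive.

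**2. Where exposure is greatest.** Section 7.1.1 specifies the last-month CAPS-5. Visits 8 and 13 fall 18 to 30 days after an Experimental Session, so that session usually lies inside the recall period. Visit 19 falls 42 to 70 days after the last session, so no session does. Talk of a session is therefore more likely at Visits 8 and 13.

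Those ratings enter the primary MMRM (SAP 8.7.1). The test, however, is the Visit 19 contrast. With a treatment-by-visit term and unstructured covariance, the earlier ratings bear on it mainly through participants who lack a Visit 19 rating. A shift confined to Visits 8 and 13 would reach the primary result only in part. A second path is that nothing stops a rater who heard a disclosure early from rating the same participant at Visit 19.

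**3. Illustration of size.** The bias is assumed, since the documents give none.

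Inputs from Protocol 14.1 and SAP 7.0: 47 per group, alpha 0.0499, final mean changes 37.4 and 20.5, variances 335 and 280. The CAPS-4 to CAPS-5 factor is 20/34 (SAP 7.0).

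Reproducing the stated 90% power:
- SD = √(335 + 280) = 24.80; difference = 37.4 − 20.5 = 16.9
- SE = 24.80 × √(2/47) = 5.12; 16.9/5.12 = 3.30
- Power ≈ Φ(3.30 − 1.96) = 91.0%, or 90.5% with the noncentral t. The SD is therefore consistent with the plan.

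On the CAPS-5 scale, SD = 24.80 × 20/34 = 14.59. SAP Table 6 implies a second value: 7.2/0.40 = 18.

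With no true effect and a net rating shift of b points toward MDMA, in a single-visit two-sample approximation:

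P(reject) = 1 − Φ(1.96 − b/SE) + Φ(−1.96 − b/SE), where SE = SD × √(2/47), that is 3.01 or 3.71.

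| b (assumed) | SD 14.59 | SD 18 |
|---|---|---|
| 0 | 5.0% | 5.0% |
| 1 | 6.3% | 5.8% |
| 2 | 10.2% | 8.4% |
| 3 | 16.9% | 12.7% |

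**The case against.** A reader might infer that the rater blind is unprotected and cannot be checked. The documents do not support that.

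- **Protection.** The interview is remote, neutral and scripted, and Section 7.1.1 limits departures from the script and rapport. Raters see no site data and are not told the full design. This stands. Apart from the script, though, these measures close routes other than disclosure by the participant.
- **Checkability.** Inclusion criterion 4 requires agreement to recording of rater assessments, and Protocol Table 5 ticks recording at Visits 8, 13 and 19. Where recordings exist, disclosures could be reviewed. What holds is that no such review is planned.
- **Silence is not permission.** Nothing invites participants to describe effects, and those who attended Visits 8 or 13 were already told to withhold the visit count. The raters' CAPS-5 training manual, cited in Section 7.1.1, is not available here and may say more.
- **Visit 19 timing and session count.** Both points stand, as shown in the working: Visit 19 lies outside the recall period for any session, and the missing visit count does little harm to the between-arm comparison by itself.
- **Timing of a change.** SAP 8.7.2 dates the interim cutoff 11 March 2020, and the current protocol amendment is dated 22 May 2020. The interim was to use about 60 participants with a final CAPS-5, so by the plan many ratings would predate a new form item.

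None of this explains why Sections 8.4.2 and 9.4 are narrower than 8.3.4, or supplies an instruction on effects and side effects.

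**Conclusion.** The point holds as an inexpensive improvement that should be made. The Visit 19 instruction is narrower than the one for Visits 8 and 13. At no visit does the instruction reach session experiences, drug effects or side effects, although the protocol promises raters who are blind to number of treatments and unaware of adverse events. No check of the rater blind is planned.

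The size is unknown. The rejection rates above rest on an assumed net shift at Visit 19, no true effect and a two-sample approximation to the MMRM. They show what a small shift would cost, not that one will occur. The text comparison does not depend on them.

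**What to change.** 1. **One instruction in Protocol 8.3.4, 8.4.2 and 9.4.** Participants answer every symptom question fully. They withhold their opinion on treatment, the number of visits or sessions, what happened in Experimental Sessions, and effects or side effects they attribute to the capsules. They report those to the site team as usual. Safety concerns are exempt.
2. **One item on the rater's source record, completed after scoring.** It records whether any such disclosure occurred (yes/no) and the rater's guess of arm.
3. **SAP.** Tabulate the item by arm and visit as a descriptive check of the rater blind. Any MMRM run without flagged ratings should be labelled exploratory. Disclosure is a post-randomization event that may depend on arm and outcome, so a changed estimate would not by itself show rater bias. A guess may likewise reflect observed improvement.
4. **Optional.** After a disclosure at Visit 8 or 13, assign that participant's later ratings to another rater. This does nothing for a disclosure at Visit 19.

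**Cost.** Aligned wording, one form item and one table. Sample size, power and alpha are unchanged. The item may prompt raters to think about the arm, which completing it after scoring limits. Data will be incomplete for participants rated before the change, and the report should say so.

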8.4.3 Study Termination

Study Termination (Visit 20) will take place 1 to 9 days after the final CAPS-5 assessment (Visit 19). Participants who have withdrawn from treatment but have continued for follow-up will also complete this assessment immediately upon withdrawal.

The site team will:

- Inquire about any possible changes in health. Assess the participant's mental health and the status of any previously recorded AEs. Record AEs as described in [Section 11.0 Safety](#).
- Inquire about concomitant medication use and adherence.
- Administer Since Last Visit C-SSRS.
- Measure weight (used to calculate BMI).
- Measure blood pressure.
- Provide and discuss a study exit plan.
- Ask them to enroll into the LTFU extension study with a visit at 12 months after the last Experimental Session. Review contact information and Informed Consent procedures for LTFU.
- Review potential timeline until study unblinding and how they will be informed of their treatment group at that time.
- Actively support participant in completion of Study Termination self-reported measures. Completion of the measures does not need to be recorded.
 - LEC-5
 - BDI-II
 - CPGS
 - EQ-5D-5L
 - IASC
 - IPF
 - SCS
 - TAS-20
 - AUDIT
 - DUDIT
 - SRNU
 - EAT-26
 - HPQSF

After all Study Termination measures and assessments are completed, the participant is considered terminated from the study. The participant can resume normal everyday life. The study team will provide an Exit Plan, which may include a referral for additional medical or therapeutic care, as described in [Section 8.4.3.2 Exit Plan](#). Eligible participants will be asked to participate in the LTFU extension study, described in [Section 8.4.3.1 Extension Studies](#).

8.4.3.1 Extension Studies

Upon completion of the study, defined as completing at least one Experimental Session and one CAPS assessment beyond Baseline, participants will be asked to join the LTFU extension study. The ICF for this study will be provided to eligible participants at the Study Termination visit. This study will measure outcomes 12 months after the last Experimental Session.

Upon unblinding after database lock, all participants who were assigned to placebo (regardless of final CAPS-5 scores), completed the study, meet criteria, and are in good standing with the clinical site, will be offered the opportunity to enroll in an open-label safety study using the same manualized MDMA-assisted psychotherapy as administered during the study. This open-label safety study will take place at least 18 months after the first participant is enrolled in MAPP1 and will last 19 to 38 weeks, similar to this protocol. Data from this study will be included in the sponsor's overall safety database.

Any sub-studies other than what is outlined in [Appendix A](#) will be detailed in separate documents.

